9.2.3. Study Population

9.2.3.1. Identification of Current Tofacitinib Users

As this study aims to assess the effectiveness and safety of RZV among patients receiving ongoing treatment with tofacitinib, we will identify current users of tofacitinib rather than new users or initiators as the source population to identify patients with and without RZV vaccine.

A patient will be considered to be a current user of tofacitinib if they have a tofacitinib on-treatment period on or after 20 October 2017. The date of tofacitinib dispensing will serve as the first day of the on-treatment period. The duration of the on-treatment period will be defined by the days' supply for the dispensing plus a grace period of 30 days to account for non-adherence. A patient will continue to be considered a current user if the time between the current and subsequent dispensing of tofacitinib is less than or equal to the days' supply plus 30 days. Otherwise, the on-treatment period will cease at the end of the 30-day grace period, and the patient will no longer be considered a current user of tofacitinib. (It should be noted that discontinuation of tofacitinib is not a censoring criterion. Patients who were previously included in one of the exposure cohorts while they were on-treatment for tofacitinib will continue to be followed if their tofacitinib on-treatment period ends.) If the patient restarts treatment with tofacitinib (ie, has another on-treatment period) after the end of a previous on-treatment period, the patient may be included in the study if they continue to meet the other eligibility criteria.

If there are consecutive dispensings of tofacitinib with overlapping days' supply, the duration of the on-treatment period will be the sum of the days' supply from each dispensing plus 30 days if the dose of tofacitinib is the same for both dispensings, as it is likely that this represents an early refill. However, if the dose of tofacitinib is different for the subsequent dispensing, the end date for the earlier dispensing will be set to the day prior to the dispensing date of the subsequent dispensing when calculating the duration of the on-treatment period.

Once patients who are current users of tofacitinib on or after 20 October 2017 have been identified, the source population will be restricted to those who are 18 years and older and have a diagnosis of UC or RA on or after 20 October 2016.

9.2.3.2. Exposure Cohorts

9.2.3.2.1. RZV 2-Dose Analysis

The RZV 2-dose analysis will be used to assess the primary objective for effectiveness.

Using UC patients as an example, patients who are current users of tofacitinib will be identified into the following 2 cohorts, based on receipt of RZV, as illustrated in [Figure 1](#):

1. UC RZV 2-Dose: UC patients who receive two doses of RZV; and

2. UC Comparator 2-Dose: UC patients who do not receive RZV and are time-matched (within a 4-week window) to patients in the UC RZV 2-Dose cohort.

Exposure cohorts among patients with RA will be identified using the same framework.

[figure not shown]
9.2.3.2.1.1. RZV 2-Dose Cohorts

Starting at the beginning of the study period (20 October 2017), Optum will identify the RZV 2-Dose cohorts by searching the pharmacy and medical claims records for RZV administrations among patients who are current users of tofacitinib (as defined in Section 9.2.3.1). Specifically, administrations of RZV that occur during tofacitinib on-treatment periods will be identified, as illustrated in Figure 3. A RZV administration will be defined as a second dose if a separate RZV administration is observed in the previous 1 to 6 months.⁹ Exposure to RZV will be identified as described in Section 9.3.4.

The RZV 2-Dose cohorts (UC or RA) will include patients who receive a second dose of RZV with the second dose occurring during a tofacitinib on-treatment period on or after the study initiation date. In the RZV 2-Dose cohorts, *the date of cohort entry will be set as the date of the second administration of RZV*. Additionally, to be eligible for the study, patients will have to fulfill additional criteria, as described in Sections 9.2.1 and 9.2.2.

While current tofacitinib exposure will be required at cohort entry (ie, receipt of second dose in the RZV 2-Dose cohort), the first dose of RZV will not be required to occur during a tofacitinib on-treatment period to be eligible for the RZV 2-Dose cohort. As shown in Figure 3, both example Patient 1 and Patient 2 are eligible for the RZV 2-Dose cohort at the time of receipt of the second RZV dose. Nonetheless, the main comparison will be the subgroup of patients whose treatment with tofacitinib overlaps with both doses of RZV relative to patients treated with tofacitinib who do not receive RZV (Section 9.7.3.1)

Figure 3. Examples of Patients Eligible for the RZV Cohort and/or Comparator Cohort

Tofacitinib exposed person-time
 Non-tofacitinib exposed person-time
★ First RZV administration
★ Second RZV administration

[figure not shown]
9.2.3.2.1.2. Comparator 2-Dose Cohorts

In a similar fashion to the identification of the RZV 2-Dose cohorts, Optum will identify a cohort of patients without exposure to RZV among patients who are current users of tofacitinib. To minimize the immortal time bias that may be introduced when exposure is defined based on information accrued during follow-up,¹⁴ these patients will be randomly drawn from time-matched vaccination risk sets that are defined as sequential 4-week windows during which they were eligible for inclusion in the RZV cohorts, but without any RZV exposure during the window. Matching within this narrow caliper of calendar time limits the potential immortal time introduced by using future information (ie, lack of RZV receipt) to classify patients at the time of cohort entry. A cohort entry date will be randomly selected from this time window. In addition, other factors, such as duration of tofacitinib use, will be considered for matching upon feasibility, which will be described in the statistical analysis plan (SAP).

To construct the vaccination risk sets, separate 4-week windows will be created, starting on the study initiation date (20 October 2017) through the end of the study period. Among patients who are current tofacitinib users within a given 4-week window, patients without any RZV exposure who meet the study inclusion criteria (Section 9.2.1) and exclusion criteria (Section 9.2.2) at the beginning of the 4-week window will be identified. These patients will be eligible to be sampled as comparator patients for each RZV initiator identified with receipt of a second RZV dose during the same 4-week window. For example, as illustrated in Figure 4, patient A at the time of second RZV dose was eligible to be matched to comparator patient B and D during risk set #1, and similarly, patient B at the time of second RZV dose was eligible to be matched to comparator patient D and E during risk set #2.

Up to 2 comparators for each RZV initiator will be selected, matched on data source (ie, the Optum Research Database [ORD] or the Optum Medicare Advantage and Medicare Part D [MA-PD] Database) and other factors considered upon feasibility. Patients will be sampled with replacement. This process will be repeated for each 4-week window during the study period; as such, it is possible that a patient could be sampled as a comparator multiple times during the study. If patients are selected more than once into the study, it will be accounted for in the statistical analysis (Section 9.7.3).

Figure 4. Example of Time-Matched Vaccination Risk Sets in the RZV 2-Dose Analysis

If a patient selected for the comparator cohort subsequently receives RZV, their follow-up time within the comparator cohort will be censored upon the date of first administration of RZV. The patient may then be included in the RZV cohorts if they still meet all eligibility criteria. Consequently, patients are eligible to contribute person-time to the RZV cohort, the comparator cohort, or both the comparator cohort and (if subsequently vaccinated) the RZV cohort. Once a person contributes person-time to the RZV cohort, they are no longer eligible to contribute to the comparator cohort.

Patients with and without RZV exposure will be included in the UC RZV cohort and UC Comparator cohort, respectively, if they have at least one medical claim with a diagnosis of UC (International Classification of Diseases, 10th revision [ICD-10] code: K51*) in any position in the 365 days prior to and including their cohort entry date. Similarly, patients with and without RZV exposure will be included in the RA RZV cohort and RA Comparator cohort, respectively, if they have at least one medical claim with a diagnosis of RA (ICD-10 code: M05*) in any position in the 365 days prior to and including their cohort entry date. In addition, M06* (other rheumatoid arthritis) will also be used, except M06.1 (adult-onset Still’s disease) and M06.4 (inflammatory polyarthropathy). If a patient has claims with both UC and RA diagnoses in the 365 days prior to cohort entry, the claim closest to the cohort entry date will be used for cohort assignment.

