Optum will identify patients in the UC and RA Comparator ≥ 1 Dose cohorts in a similar fashion used to identify UC and RA Comparator 2-Dose cohorts, as described in Section 9.2.3.2.1.2. These patients will be randomly drawn from time-matched vaccination risk sets that are defined as sequential 4-week windows during which they were eligible for inclusion in the RZV ≥ 1 Dose cohorts, but without any RZV exposure during the window. These patients will be eligible to be sampled as comparator patients for each RZV initiator identified with receipt of a first RZV dose during the same 4-week window. For example, as illustrated in [Figure 5](#), patient A at the time of first RZV dose was eligible to be matched to comparator patient B, C, and D during risk set #1, and similarly, patient C at the time of first RZV dose was eligible to be matched to comparator patient B and D during risk set #2. A cohort entry date will be randomly selected from within this time window. Up to 2

comparators for each RZV initiator will be selected, matched on data source (ie, the ORD or the MA-PD Database) and other factors considered upon feasibility.

Figure 5. Example of Time-Matched Vaccination Risk Sets in the RZV ≥ 1 Dose Analysis

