9.5. Study Size

[figure not shown]
Table 1 displays the counts of patients with RA and UC, and with RZV and tofacitinib exposure, that were observed in the ORD and MA-PD between October 2017 and December 2022. This count is for informational purposes only. Final sample size for the study could change depending upon criteria applied during the conduct of the protocol and required approvals.

Table 1. Counts of Tofacitinib and RZV Recipients Among Adults (18+) with RA or UC: ORD and MA-PD October 2017 to December 2022

Patient Characteristics	N
Patients with RA	446,618
Patients with UC	202,619
Patients with RA and/or UC	639,868
With a dispensing of tofacitinib	12,491
With receipt of RZV	100,005
With a dispensing of tofacitinib and receipt of at least one dose of RZV	2,744
With a dispensing of tofacitinib and receipt of two doses of RZV	1,932

Of the 2,744 tofacitinib users with RA or UC who received at least one dose of RZV, there were 1,932 (70%) who received two doses of RZV. These patients had a median of 11 tofacitinib dispensings, suggesting that there may be a subset of patients with tofacitinib exposure that overlaps both RZV doses. Assuming a background rate of HZ of 1.2 cases per 100 person-years among non-tofacitinib exposed patients with UC and RA²⁵ and an effectiveness of RZV in preventing HZ of 85%²⁶ among non-tofacitinib exposed patients with RA or UC, the sample size necessary to exclude 85% from the 95% confidence interval for the RZV effectiveness estimate for tofacitinib exposed patients with RA or UC was calculated. Figure 6 displays the upper bound of the 95% confidence interval for a range of estimated vaccine effectiveness and population sizes. Thus, for 2,000 RZV-exposed person-years, the upper 95% confidence interval bound of vaccine effectiveness would exclude 85% if the point estimate among tofacitinib exposed patients with RA or UC were 66.7% or lower (corresponding to an effect size of 21.5%, meaning that tofacitinib reduces the RZV effectiveness by 21.5%). For 4,000 RZV-exposed person-years, the estimated 95% confidence interval would exclude 85% if the point estimate among tofacitinib exposed patients with RA or UC were 70.8% or lower (corresponding to an effect size of 16.7%, meaning that tofacitinib reduces the RZV effectiveness by 16.7%). These estimates are generated for a range of plausible population sizes based on Optum feasibility counts shown in Table 1.

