Figure 6. Upper Bound of Vaccine Effectiveness for a Range of Population Sizes and Vaccine Effectiveness Estimates

Assumptions: 1.2% HZ rate in unexposed; 2:1 matching of comparators to RZV exposed patients²⁷

Table 2. Prevalence of Zostavax Vaccination and Duration of Enrollment Among Adults (18+) with RA or UC Treated with Tofacitinib and Shingrix: Optum Claims Database, October 2017 to July 2022

	Patients with Tofacitinib and Shingrix	
	Patients <60 years of age N (%)	Patients ≥60 years of age N (%)
Total patients	649 (100.0%)	1,248 (100.0%)
Patients with a claim for Zostavax^a	16 (2.5%)	94 (7.5%)
With at least 1 year of enrollment prior to Shingrix ^a	544 (83.8%)	1,069 (85.7%)
Patients with a claim for Zostavax^b	16 (2.9%)	87 (8.1%)
With at least 2 years of enrollment prior to Shingrix ^a	437 (67.3%)	859 (68.8%)
Patients with a claim for Zostavax^b	15 (3.4%)	83 (9.7%)
With at least 3 years of enrollment prior to Shingrix ^a	340 (52.4%)	667 (53.5%)
Patients with a claim for Zostavax^b	13 (3.8%)	74 (11.1%)
With at least 4 years of enrollment prior to Shingrix ^a	264 (40.7%)	519 (41.6%)
Patients with a claim for Zostavax^b	10 (3.8%)	68 (13.1%)
With at least 5 years of enrollment prior to Shingrix ^a	205 (31.6%)	388 (31.1%)
Patients with a claim for Zostavax^b	7 (3.4%)	52 (13.4%)

^a Denominator for percent is the number of patients in the relevant age category (<60, ≥60).

^b Denominator for percent is the number of patients with the duration of enrollment (eg, 1, 2, etc) in the row above.

The prevalence of prior Zostavax vaccination and duration of enrollment among UC and RA patients treated with tofacitinib and Shingrix is shown in [Table 2](#). Among patients under age 60 years, 2.5% had prior exposure to Zostavax whereas 7.5% of patients 60 years of age and older had Zostavax exposure. Regarding duration of enrollment prior to receipt of Shingrix, over 80% of patients in both age groups had at least 1 year, while slightly more than 30% had at least 5 years of enrollment.

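### The cap of two comparators per vaccinee could be raised to five at low cost; the gain is modest and falls mainly on the secondary flare analyses

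*Protocol*

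**What the plan says.** Section 9.2.3.2.1.2 builds the 2-dose comparators from sequential 4-week risk sets: "Up to 2 comparators for each RZV initiator will be selected, matched on data source", plus other factors if feasible. It adds: "Patients will be sampled with replacement". Section 9.2.3.2.2.2 uses the same scheme for the ≥1 dose cohorts, again with up to two "comparators for each RZV initiator will be selected, matched on data source". The sizing in Section 9.5 follows suit; the note under Figure 6 reads "Assumptions: 1.2% HZ rate in unexposed; 2:1 matching of comparators to RZV exposed patients".

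The protocol gives no purpose for the number two. Section 9.2.3.2.1.2 credits protection against immortal time to the narrow calendar windows. Section 9.7.2 leaves confounding control to ATT weights, which are one for vaccinees and e/(1−e) for comparators. Section 9.6 describes a single extraction of existing data. Sections 9.7.3.1 and 9.7.3.2 account for repeated selection of a person only if such repeats exceed 10% of the study population.

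**The concern.** In a claims study, an extra comparator already in the data needs no new data collection. A cap that omits eligible comparators at random before weighting therefore gives up some precision, and ATT weighting lowers the effective number of comparators again.

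How much this matters depends on which arm drives the variance. For herpes zoster the vaccinated arm has few events and dominates. For flare, with similar rates in the two arms, the comparator side carries a larger share. Flare is the safety question: follow-up stops at 90 days, UC and RA are analysed separately, and Section 9.5 gives no precision for it. A reassuring answer on flare depends on how tight the upper confidence limit is.

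**Working it through.** **Inputs.** From Section 9.5: "Assuming a background rate of HZ of 1.2 cases per 100 person-years among non-tofacitinib exposed patients with UC and RA"; a reference effectiveness of 85%; 2,000 or 4,000 RZV-exposed person-years; 2:1 comparators. From Table 1: 12,491 tofacitinib users, 2,744 with at least one RZV dose, 1,932 with two. Assumed here, because the protocol gives no figure: a flare hazard ratio near 1, and a weighting loss shown at none and at one half.

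**The plan's own figure.** At 2,000 exposed person-years, 4,000 comparator person-years yield 48 events, and 24 events would be expected in vaccinees without protection. Eight vaccinated events give effectiveness 1 − 8/24 = 66.7%. The upper 95% bound is 84.2% (Wald) or 84.96% (Jeffreys-type). Seven events (70.8%) give 86.8% and 87.5%, so 66.7% reproduces. At 4,000 person-years, 14 against 96 events give 70.8% with an upper bound of 83.8% (Jeffreys-type), as stated. The mid-P and Fisher bounds for 8 against 48 are 85.3% and 86.4%, so the first threshold depends on the interval used.

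**Formula.** With k comparators per vaccinee, rate ratio RR and weighting loss factor D (1 = none, 2 = effective comparators halved), SE(log RR) is proportional to √(1/RR + D/k). The ratio of standard errors between two values of k does not depend on the person-years, so it applies to UC and RA separately.

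**Flare, RR = 1, from 2:1 to 5:1.**
- D = 1: √(1.2/1.5) = 0.894, or 11% lower.
- D = 2: √(1.4/2.0) = 0.837, or 16% lower.
- Comparator share of the variance at 2:1: 0.5/1.5 = 1/3 with D = 1, and 1/2 with D = 2.

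**Herpes zoster, effectiveness 70%, 2,000 person-years.** Vaccinated events: 24 × 0.3 = 7.2. Comparator events: 24k/D.

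| | 2:1 | 5:1 | Change |
|---|---|---|---|
| D = 1 | √(1/7.2 + 1/48) = 0.400 | √(1/7.2 + 1/120) = 0.384 | −4% |
| D = 2 | √(1/7.2 + 1/24) = 0.425 | √(1/7.2 + 1/60) = 0.394 | −7% |

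**Effect on the sizing threshold, no weighting loss.** At 2,000 person-years and 5:1, eight events still exclude 85% and seven still do not (upper bound 86.4% Wald, 87.2% Jeffreys-type). The 66.7% threshold does not move. On a continuous Wald scale it moves from 67.9% to 68.7%, with a limit of 69.2% for unlimited comparators.

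**Room above two.** Users without RZV: 12,491 − 2,744 = 9,747. That is 9,747/2,744 = 3.6 persons per ≥1-dose vaccinee and 9,747/1,932 = 5.0 per 2-dose vaccinee. The study period of about 75 four-week windows lets one person serve in several. Slots needed at 5:1 are 5 × 2,744 = 13,720 in the ≥1 dose analysis, more than the 9,747 persons, and 5 × 1,932 = 9,660 in the 2-dose analysis. Both comparisons are before eligibility rules. Vaccinees' own time before vaccination adds some.

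**The case against.** The cap is stated openly, is the same in both analyses and is carried into the sizing. Nothing is contradicted and no bias follows. That stands: this is a choice that can be improved, not an error.

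The calculation treats each draw as new information. Herpes zoster follow-up runs to disenrollment, death, study end or RZV receipt and does not stop when tofacitinib stops. A later draw of the same person is therefore largely nested in the earlier one and shares the same event. The slot counts show that reuse would be frequent. This stands, and it makes every figure above an upper bound; a robust variance corrects the standard error but does not create information. The 90-day flare windows overlap much less, though they remain within person.

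Table 1 is given for information only and precedes the on-treatment, enrollment, prior-zoster, prior-flare and data-source restrictions, so the usable ratio is unknown. This also stands. Wording the cap as up to five copes with thin windows.

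Three stronger readings are tempting, and the protocol supports none of them.
- *The primary objective is underpowered because of the cap.* Vaccinated-arm events dominate the variance, and the stated threshold does not move.
- *The cap buys nothing.* Section 9.2.3.2.1.2 leaves matching on further factors, such as duration of tofacitinib use, open to feasibility, and a higher ratio makes close matching harder.
- *More comparators would improve overlap or tame extreme weights.* Extra random draws from the same risk sets leave the covariate distribution unchanged in expectation. They multiply e/(1−e) by a constant, so relative weights stay as they are.

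**Conclusion.** The point holds as a low-cost precision gain, chiefly for the secondary flare analyses. From 2:1 to 5:1, the flare standard error falls by at most about 11% with a hazard ratio near 1 and no weighting loss. The 16% figure rests on the assumption that ATT weighting halves the effective comparators, for which the protocol gives no value. For herpes zoster the ceiling is about 4% at 70% effectiveness (7% under the same assumption), and overlapping follow-up makes the real gain smaller.

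The protocol gives no flare rate, so only a relative gain can be stated. It cannot be said from this document that flare precision at 2:1 is inadequate.

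**What to change.** In Section 9.2.3.2.2.2, and for consistency in Section 9.2.3.2.1.2, select up to five comparators per vaccinee as eligibility and matching allow. Taking all eligible users in each risk set is an alternative if they are weighted so that the calendar-time mix still follows the vaccinees. In Sections 9.7.3.1 and 9.7.3.2, use a person-clustered robust variance in the weighted Cox models in every case, in place of the 10% trigger. Restate the assumption "2:1 matching of comparators to RZV exposed patients" under Figure 6 and redraw the figure.

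The costs are programming, a small protocol and sizing update, more repeated use of the same persons, and less room for tight matching on extra factors. If matching on tofacitinib duration matters more, a ratio between two and five is a reasonable compromise. Fix the number before outcomes are examined.

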9.2.3.2.2. RZV ≥ 1 Dose Analysis

The RZV ≥ 1 dose analysis will be used to assess the secondary objectives for effectiveness and safety.

Separate cohorts will be created to address the secondary objectives for effectiveness and safety comparing patients who receive at least one dose of RZV to patients who do not receive of RZV. Using patients with UC as an example and similarly to the RZV 2-Dose analysis, patients who are current users of tofacitinib will be identified into the following 2 cohorts, based on receipt of RZV, as illustrated in [Figure 1](#):

1. UC RZV ≥ 1 Dose: UC patients who receive at least one dose of RZV; and
2. UC Comparator ≥ 1 Dose: UC patients who do not receive RZV and are time-matched (within a 4-week window) to patients in the UC RZV ≥ 1 Dose cohort.

Exposure cohorts among patients with RA will be identified using the same framework.

9.2.3.2.2.1. RZV ≥ 1 Dose Cohorts

Starting at the beginning of the study period (20 October 2017), Optum will identify the RZV ≥ 1 Dose cohorts by searching the pharmacy and medical claims records for RZV administrations among patients who are current users of tofacitinib (as defined in Section 9.2.3.1). Specifically, administrations of RZV that occur during tofacitinib on-treatment periods will be identified, as illustrated in [Figure 3](#). Exposure to RZV will be identified as described in Section 9.3.4.

[figure not shown]
In the RZV ≥ 1 Dose cohorts (UC or RA), *the date of cohort entry will be set as the date of the first administration of RZV during a tofacitinib on-treatment period on or after the study initiation date, with no administration of RZV in the prior 365 days.* Additionally, to be eligible for the study, RZV initiators will have to fulfill additional criteria, as described in Section 9.2.1 and 9.2.2 and shown in [Figure 2\(b\)](#).

9.2.3.2.2.2. Comparator ≥ 1 Dose Cohorts

Optum will identify patients in the UC and RA Comparator ≥ 1 Dose cohorts in a similar fashion used to identify UC and RA Comparator 2-Dose cohorts, as described in Section 9.2.3.2.1.2. These patients will be randomly drawn from time-matched vaccination risk sets that are defined as sequential 4-week windows during which they were eligible for inclusion in the RZV ≥ 1 Dose cohorts, but without any RZV exposure during the window. These patients will be eligible to be sampled as comparator patients for each RZV initiator identified with receipt of a first RZV dose during the same 4-week window. For example, as illustrated in [Figure 5](#), patient A at the time of first RZV dose was eligible to be matched to comparator patient B, C, and D during risk set #1, and similarly, patient C at the time of first RZV dose was eligible to be matched to comparator patient B and D during risk set #2. A cohort entry date will be randomly selected from within this time window. Up to 2

comparators for each RZV initiator will be selected, matched on data source (ie, the ORD or the MA-PD Database) and other factors considered upon feasibility.

Figure 5. Example of Time-Matched Vaccination Risk Sets in the RZV ≥ 1 Dose Analysis

